1.2 Outcomes

The main outcomes regarding the Clinical Study Dossier and clinical study procedures are summarised below.

Inclusion and exclusion criteria

The definition of inclusion and exclusion criteria is based on an extensive literature review and the internal Al-Mind partners` agreement to adhere to the project's objectives.

Definition of MCI at enrolment

General consensus of the criteria to define MCI for the clinical study participants. The inclusion criteria define the degree of cognitive impairment and a minimum of test assessments (table 2).

Ethical requirements and Informed Consent before enrolment

All clinical sites followed the local ethical procedures in alignment with relevant national and EU laws and regulations. An independent Al-Mind ethics advisor has been appointed. Feedback from the user representing association Alzheimer Europe has been implemented.

Ethical Committee approvals

The study has been approved by the Ethical Committees of all clinical sites in due course. The final consensus of the used clinical guidelines, procedures and formation have been incorporated into the application. All Informed Consents have been approved.

Definition of demographic and clinical data collection

Various clinical variables (e.g. demographics, weight, etc.), information about well documented associated pathologies and interventions will be collected. These data will be analysed in order to determine their influence on the risk of progression to dementia for population with MCI.

Blood sample collection, storage and shipment

Blood samples will be collected at the first visit, to determine their APOE allele constellation and individual P-Tau associated P181 and/or P217 protein levels. The samples will be collected, stored and shipped according to standardised procedures (Deliverable 2.1).

Harmonisation of EEG recording and storage

All technological aspects for the EEG recording have been standardised and agreed on among the experts from the five clinical sites. All sites will use identical 128-channel EEG devices and harmonised recording parameters (amplification, sampling rate, filters, artefact recognition, duration of each session etc). The characteristics of the recording environment (baseline noise/light brightness) have been standardised (Deliverable 2.1).

Digitalised Cognitive Testing (CANTAB)

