3.1 Summary

The aim of this observational, naturalistic study is to validate AI-based tools used for an innovative approach to early dementia risk estimation.

Today, we know that about 50% of patients with MCI are at risk of developing dementia. Early risk signs include functional brain network disturbances as an expression of synaptic dysfunction/failure in the earliest course of potential dementia development. This synaptic dysfunction can be explored by electrophysiological brain signals. The Al-Mind Connector algorithm will identify such functional brain networks in an automated manner using the Graph theory, among other mathematical possibilities. Classical machine and deep learning approaches of artificial intelligence will be deployed by automating these brain network identifications. The Al-Mind Predictor will serve as an enriched Connector, by applying prospectively data from a sample of 1000 MCI participants in a multimodal prediction method for risk estimation. Enrichment is achieved by including digital cognitive tests, APOE alleles genotyping and plasmatic P-Tau protein level information to develop the Al-Mind Predictor algorithm. The Al-Mind Predictor will discriminate between MCI-prodromal-to-dementia patients and MCI-non-prodromal-to-dementia subjects. The results of the anticipated, highly sensitive Al-Mind Predictor will be compared to state-of-the-art (SOA) approaches.

The new technology will not compete with existing diagnostic tools for dementia (CSF, fMRI, PET, SPECT), because AI-Mind wishes to take its role as an early predictive screening method, increasing the percentage of correctly selected MCI subjects for further invasive or more costly diagnostics, resulting in earlier intervention. Importantly, AI-Mind's new data handling procedures only use existing, well-established, globally accessible and low-cost SOA technologies. With AI-Mind's new data processing approach, the goal is to increase today's low predictive value (<0.5) of the SOA-based clinical dementia prediction, and proactively select with higher accuracy than before, MCI-prodromal patients for further clinical intervention. Thereby, AI-Mind wishes to contribute to delaying dementia development by detecting the risk at the first visit when symptoms occur.

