3.7 Instrumental clinical procedures

In this subchapter, the used instrumental clinical procedures are briefly presented. For specific technical details of these procedures, refer to Deliverable 2.1.

Electroencephalography

Empowered EEG recordings will be done at all clinical sites. Resting state (RS) data (three times five-minute intervals; eyes-open, eyes-closed, eyes-open) will be recorded by a 128-channel device, identically procured at all the centres². EEG data will be pre-processed using a semi-automatic pipeline defined in WP2, including SOA procedures for detection and management of signal noise and other artefacts. Moreover, a set of programmed and voluntary reproduced artefacts will be collected at the beginning of each session (harmonised procedures for all clinical centres in order to better identification).

Magnetoencephalography

MEG recordings will be done at two clinical sites: HUS and UCM. MEG recordings will be performed using standard procedures (Gross et al., 2013) with MEGIN systems (306-channel). Data will be collected at a sampling frequency of 2000 Hz and online band-pass filtered between 0.1 and 660 Hz. The MEG protocol will be identical with the EEG protocol. MEGs will be recorded at two-time points (visits 1 and 4). MEG and EEG measurements are conducted simultaneously.

Genetic and protein analysis

Blood sample for DNA isolation and plasma protein assessment will be collected from participants in the morning of the first visit, with participants non-fasting. Collection, storage, and shipment procedures have been standardised by the "Standard Operating Procedure" authored by the responsible blood analysing partner OUS (see Deliverables 2.1 and 9.4).

Genetic analysis of the $\epsilon 4$ allele of APOE is the strongest genetic risk factor for AD compared to those carrying the more common $\epsilon 3$ allele (Lambert JC, et al., 2009; Corder et al., 1994). The presence of this allele is associated with increased risk for both early-onset and late-onset AD, while allele ϵ 2 is protective. In the future AI model, the genetic data will be beforehand classified either as increased-risk or not. The determination of phosphorylated form of tau (P- tau 181) may increase the specificity and sensitivity in the detection of AD. Other genetic biomarkers, that may eventually stem from research during the course for the AI-mind project, will be potentially added for further evaluation (besides ApoE and P-Tau 181, -217).

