In addition, a cross-WP meeting (breakout session WP2 & 5) took place within the frame of the 3rd General Assembly (Oslo, 17 September 2021). The outcome of the meeting was the final agreement on the previously discussed clinical criteria, neuropsychological assessment proposals for screening and recruitment strategies. Furthermore, as mentioned earlier (chapter 3.7) the classical neuropsychological investigation for comparison and validation of the digitalised CANTAB testing was negotiated and standardised.

5 Statistical aspects and power calculation

It is assumed that AI-Mind Predictor will achieve specificity and sensitivity > 0.9 in the targeted population, in which the approximate prevalence of both 'prodromal-to-dementia' and 'nonprodromal-to-dementia' is about 50%. We explored the sample size required for the ability to verify the measures of the predictive performance, i.e. the sizes of both validation and test data sets. The sample size calculations have been carried out for the specificity and sensitivity estimates by simulating the appliance of the binary classifier to a simulated dataset of total N subjects, fixing the performance of the classifier to specificity = sensitivity = 0.9, as the lower bound case will result in largest variability of the results. Due to symmetry caused by the equal prevalence of prodromal/non-prodromal and specificity = sensitivity, and the confidence intervals will be equal for sensitivity and specificity estimators. The width of the $(1 - \alpha)$ -confidence interval of the estimated classifier sensitivity and specificity is used to determine the accuracy of the estimates given sample size N. One thousand participants and 4000 repetitive measurements had been calculated as sufficient for reaching the Al-Mind goal to achieve a specificity and sensitivity > 0.9. Furthermore, the definition for each participant analysis set should be defined at the participant level. To implement the estimated framework, defined analysis data sets will be defined (table 4) that specify the set of data used in the analysis for a given estimate (or family of estimates that differ only in endpoint) based on how key intercurrent events will be handled for that estimate. For these purposes of analysis, the following analysis sets have been defined:

Table 4: Defined analysis data sets

Defined Analysis Data Sets	Description
Training set	Participants not included in the test set and randomised to the model building set.

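### APOE is reduced to two risk classes before modelling, although the full genotype is measured and the protocol itself calls ε2 protective: a minor, cheaply avoided loss of information

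*Protocol*

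**What the plan says.** Protocol section 3.7, under genetic and protein analysis, says of ε4: "The presence of this allele is associated with increased risk for both early-onset and late-onset AD". It adds "while allele ϵ 2 is protective". Its next sentence fixes the model input: "the genetic data will be beforehand classified either as increased-risk or not".

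The blood sample is taken "to determine their APOE allele constellation" (section 1.2), so all six genotypes can be distinguished. Section 3.1 lists the enrichments that turn the Connector into the Predictor as "including digital cognitive tests, APOE alleles genotyping and plasmatic P-Tau protein level information".

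The protocol does not say which genotypes fall in the increased-risk class, where ε2/ε4 belongs, or why two classes were chosen. It gives no allele frequency and no odds ratio.

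**The concern.** The text names three directions of risk (ε4 up, ε3 as reference, ε2 down) and then commits to two classes before any model is fitted. Merging categories can never add information, and it loses some whenever risk differs within a merged class. If ε2 protects, as the protocol says, risk does differ inside the class that is not increased-risk: ε2 carriers and ε3/ε3 share one value.

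Two things are at stake. First, a marker chosen to enrich the Predictor would enter in weakened form although the finer data are already in hand. Second, because the class is undefined, two analysts could build different variables from the same sentence, most obviously for ε2/ε4.

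This is a coding choice that the protocol states, not a detail it leaves open.

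**Working it through.** **The plan's own figures.** The protocol gives no figure for the effect of the coding. Its sample-size figure (1000 participants, 4000 measurements; section 5) does not depend on APOE coding. It also cannot be reproduced, since α, the target interval width and the test-set share are given no values. Section 5 supplies two inputs used below: "approximate prevalence of both 'prodromal-to-dementia' and 'nonprodromal-to-dementia' is about 50" percent, and "fixing the performance of the classifier to specificity = sensitivity = 0.9".

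**Assumptions (none in the protocol).** Hardy-Weinberg genotypes; ε4 frequency 0.15–0.30; ε2 frequency 0.05–0.08; odds ratio (OR) per ε4 allele 1.8–2.5; OR for ε2 carriers 0.5–0.7; progression 20–50%. Increased-risk is read as ε4 carrier.

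**Formulas.**
- Genotype frequencies f: squares and doubled products of the allele frequencies.
- Risk p = 1/(1 + exp(−b − ln OR)), with b solved so that Σ f·p equals the progression rate π.
- Information I = H(π) − Σ f·H(p), where H(p) = −p ln p − (1−p) ln(1−p). For the two-class input, f and p are those of the merged classes.
- Loss = 1 − I(two-class)/I(full genotype).

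**One scenario in full.** ε2 = 0.05, ε3 = 0.75, ε4 = 0.20, π = 0.5, OR 0.6 for ε2 carriers, 2 for one ε4 and 4 for two. The solution is b = −0.223.

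| Genotype | f | p |
|---|---|---|
| ε2/ε2 | 0.0025 | 0.324 |
| ε2/ε3 | 0.0750 | 0.324 |
| ε3/ε3 | 0.5625 | 0.444 |
| ε2/ε4 | 0.0200 | 0.490 |
| ε3/ε4 | 0.3000 | 0.615 |
| ε4/ε4 | 0.0400 | 0.762 |

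The flag gives 36% carriers with risk 0.625 and 64% non-carriers with risk 0.430. I(full) = 0.02220 and I(two-class) = 0.01762, so the loss is 1 − 0.01762/0.02220 = 21%. AUC for APOE alone falls from 0.606 to 0.590. With no dose effect (two ε4 copies also OR 2), the loss is 1 − 0.01475/0.01743 = 15%, and AUC falls from 0.594 to 0.582.

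**Over the assumed ranges.**

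| Case | Loss, median | Loss, range | Fall in AUC, APOE alone |
|---|---|---|---|
| ε4 dose effect | 23% | 11–41% | 0.011–0.039 |
| No dose effect | 14% | 4–42% | 0.006–0.029 |

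**Wider assumptions.** With ε2 frequency 0.03–0.08, ε4 frequency 0.12–0.30, ε2 OR 0.4–1.0 per allele, one-copy ε4 OR 1.5–4, two copies from no dose effect up to the square of that OR, and progression 0.2, 0.3 or 0.5, there are 1296 scenarios. The median loss is 12%, the 5th–95th percentile is 0–49%, and the extremes are 0 and 73%. The loss is zero only if ε2 has no effect and ε4 has no dose effect.

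**People affected.** ε2 without ε4 is f(ε2/ε2) + f(ε2/ε3) = ε2² + 2·ε2·ε3. That gives about 67 per 1000 (ε2 0.05, ε4 0.30) to 130 per 1000 (ε2 0.08, ε4 0.15). ε4/ε4 is 0.15² to 0.30², about 22 to 90 per 1000.

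**Effect on the Predictor.** The genotype's log-likelihood ratio was added to an independent normal score standing for all other inputs, in five illustrative scenarios at 50% prevalence.
- Other inputs strong (AUC alone 0.955, Predictor near 0.9): the gain in sensitivity = specificity from the full genotype is 0.0001–0.001 in four scenarios. It is 0.004 (0.9014 against 0.8975) in the most extreme one: ε2 OR 0.4, ε4 OR 4 and 16.
- Other inputs weak (AUC alone 0.76): the gain is 0.0005–0.0035 in four scenarios and 0.011 in the extreme one, but the Predictor then reaches only 0.70–0.76.

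For scale, the 95% half-width is 1.96·√(0.9·0.1/500) = 0.026 if all 1000 are tested, and 1.96·√(0.09/100) = 0.059 if 200 are.

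**The case against.** **The class is not defined.** The e4-carrier reading is an inference; ε2/ε4 could be placed in either class. This stands. It limits what can be said about particular mergers, but any two-class coding of six genotypes pools some of them.

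**The dose effect is not in the protocol.** Section 3.7 speaks only of the presence of ε4, and its statements concern Alzheimer's disease risk rather than progression in people who already have MCI. This stands, and it is why the no-dose case is shown separately. The ε2 statement is the protocol's own, and it alone is enough for some loss if it carries over to progression.

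**Two classes do save something.** A flag needs fewer parameters and avoids sparse cells: at ε2 = 0.05, about 2.5 participants per 1000 are ε2/ε2. A reader might infer that the simplification buys nothing. That goes too far; it saves nothing in sampling or assay.

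**Feature coding belongs to later documents and is reversible.** Section 5 defers technical detail to the analysis plan, and the genotype is still measured. This lowers the severity. The two-class commitment is nonetheless written in the protocol and would carry forward unless changed.

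**The primary endpoint hardly moves.** A reader might infer that the coding puts the 0.9 target at risk. The calculation does not support that: the effect is far smaller than the sampling error of the estimates.

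**Conclusion.** The concern holds as a minor improvement. The protocol calls ε2 protective, measures the full genotype, and then fixes a two-class input whose membership it does not define.

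With increased-risk read as ε4 carrier, and under the assumed ranges, the loss is about 10–40% of APOE's own information with an ε4 dose effect, about 4–42% without one, and roughly 0–50% more widely. No single percentage can be stated as fact, because every frequency and odds ratio behind these figures is an assumption. AUC for APOE alone falls by about 0.006–0.04. The Predictor's sensitivity and specificity change by about 0.001–0.004, so the coding is not shown to decide any primary conclusion.

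**What to change.** Replace the two-class sentence in section 3.7 with a statement that APOE enters the model as the number of ε4 alleles (0, 1, 2) plus an ε2-carrier indicator, with ε2/ε4 taking both terms. Keep a two-class version as a sensitivity analysis, and list the genotypes in each class, including where ε2/ε4 falls. Settle this before model building starts.

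The cost is one sentence and one extra parameter, with no new data. The ε4/ε4 group may be sparse; the linear allele count or the model's usual shrinkage handles this, and ε2/ε2 is pooled in the indicator. The coding still simplifies: it assumes a log-linear ε4 effect and additivity for ε2/ε4. A similar four-level coding (ε2 without ε4, ε3/ε3, one ε4, two ε4) lost a median of 1.3% of the information over the wider assumptions, against 12% for the two-class flag.

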3.8 Recruitment activities

Several dissemination activities have been conducted to identify possible candidates for participation. The use of media, classical (TV, radio, etc.) and modern social media are selected as first-line field for dissemination activities: interviews have been broadcasted on major social and national channels, newspaper and magazine publications have been carried out spreading information on the project and highlighting inclusion criteria. In addition, material to support recruitment procedures has been created: the project's website for professionals and potential participants (in national languages), flyers, explanatory video etc. Finally, national recruitment resource groups and collaborations have spread information about Al-Mind among general medical practitioners and specialists, raising awareness of the project's objectives and goals.

4 Harmonisation of study procedures

The following study procedure harmonisation meetings took place before the submission of this deliverable:

- 15 April 2021: "Define minimum data set of neuropsychological investigations and pathological cut-off limits in each nation. Create the agendas and schedule the harmonisation meetings". In addition, the dissemination activities were discussed. Caregiver associations will be involved to disseminate the project among the potential participants. Clinical partners were asked to provide examples of materials for dissemination.
- 23 June 2021: clinical expert consensus meeting targeting the definition of inclusion and exclusion criteria. The WP5 leader asked each site to document which cognitive scales are routinely used and to which clinical variables would be considered essential to register in Al-Mind for designing the CRF.
- 28 September 2021: EEG/Blood sample analysis harmonisation meeting. Standards for EEG recordings had been set. A video for the reproduction of the most frequent movement artefacts had been prepared and shared with the partners. The video was delivered by IRCCS and UCSC. OUS presented the blood sample collection and shipment procedures and will share an educational video on the same topic before the beginning of study enrolment (blood sample collection and processing, samples storage and shipment).

In addition, a cross-WP meeting (breakout session WP2 & 5) took place within the frame of the 3rd General Assembly (Oslo, 17 September 2021). The outcome of the meeting was the final agreement on the previously discussed clinical criteria, neuropsychological assessment proposals for screening and recruitment strategies. Furthermore, as mentioned earlier (chapter 3.7) the classical neuropsychological investigation for comparison and validation of the digitalised CANTAB testing was negotiated and standardised.

5 Statistical aspects and power calculation

It is assumed that AI-Mind Predictor will achieve specificity and sensitivity > 0.9 in the targeted population, in which the approximate prevalence of both 'prodromal-to-dementia' and 'nonprodromal-to-dementia' is about 50%. We explored the sample size required for the ability to verify the measures of the predictive performance, i.e. the sizes of both validation and test data sets. The sample size calculations have been carried out for the specificity and sensitivity estimates by simulating the appliance of the binary classifier to a simulated dataset of total N subjects, fixing the performance of the classifier to specificity = sensitivity = 0.9, as the lower bound case will result in largest variability of the results. Due to symmetry caused by the equal prevalence of prodromal/non-prodromal and specificity = sensitivity, and the confidence intervals will be equal for sensitivity and specificity estimators. The width of the $(1 - \alpha)$ -confidence interval of the estimated classifier sensitivity and specificity is used to determine the accuracy of the estimates given sample size N. One thousand participants and 4000 repetitive measurements had been calculated as sufficient for reaching the Al-Mind goal to achieve a specificity and sensitivity > 0.9. Furthermore, the definition for each participant analysis set should be defined at the participant level. To implement the estimated framework, defined analysis data sets will be defined (table 4) that specify the set of data used in the analysis for a given estimate (or family of estimates that differ only in endpoint) based on how key intercurrent events will be handled for that estimate. For these purposes of analysis, the following analysis sets have been defined:

Table 4: Defined analysis data sets

Defined Analysis Data Sets	Description
Training set	Participants not included in the test set and randomised to the model building set.
Validation set	Participants not included in the test set and randomised to the model validation set.
Test set	Participants randomised to the model performance verification set
	and will not be used inmodel building.

Multivariate classifier methods such as multivariate logistic regression will be used to predict the binary outcome of subjects. The statistical analysis plan will describe the planned analyses in greater detail (WP3). The statistical analysis plan will include a more technical and detailed description of the statistical analyses (future WP3 deliverables).

Participants lost to follow up and dropped out

A participant will be considered lost to follow-up if he/she repeatedly fails to show up to scheduled visits and is unable to be contacted by the study site. If a participant fails to appear at the clinic for a scheduled study visit, the following must occur:

- The site personnel will attempt to contact the participant and reschedule the missed visit as soon as possible. The participant will be counselled on the importance of maintaining the visit schedule and ascertain whether the participant wishes to and/or should continue in the study.
- Before a participant is deemed lost to follow up, the investigator or designee will make every
 effort to regain contact with the participant (where possible, telephone calls and, if necessary,
 a certified letter to the participant's last known mailing address or local equivalent methods).
 These contact attempts should be documented in the participant's medical record.
- Should the participant continue to be unreachable, he/she will be considered to have withdrawn from the study (lost to follow-up).

In addition, if the participant during the 2-year follow-up develops criteria for exclusion, he/she will be informed and leave the study (drop-out).

6 Regulatory status and ethical activities

The study will be conducted according to the Declaration of Helsinki, Institutional Review Boards (21 CFR 56), Obligations of Clinical investigators (21 CFR 312) and Council for International Organizations of Medical Sciences International Ethical Guidelines (CIOMS). In addition, all clinical sites will comply with Good Clinical Practice guidelines and applicable laws and regulations.

All study records will be kept on the secure TSD server, administered by the University of Oslo, operating in accordance with the EU Data Protection Directive 95l46lEC and the General Data Protection Regulation (GDPR). The code sheets linking a patient's name to a patient identification number will be stored separately at each clinical site in each participating nation on a secure local data server. The final repository (UiO) has been approved by the local ethical committees, along with the terms of data storing (time, privileges, etc.). All nationally approved data transfers have been negotiated and documented in a Data Transfer Agreement (DTA), signed between OUS and the clinical sites (HUS, IRCCS, UCSC, UCM). All national clinical sites must comply with all applicable privacy regulations, health insurance regulations, EU Data Protection Directive 95l46lEC and the General Data Protection Regulation (GDPR).

To address the specific ethical and legal concerns on data safety and privacy in the project, seven partners in our consortium (AE, DNV, OUS, HUH, IRCCS, UCSC and TLU) have been ensuring that the AI-Mind service is in line with all applicable European and national standards and legislation. In addition, the project is supervised by the independent Ethics Advisor (Deliverable 9.5), underlining the commitment to address legal and ethical concerns regarding the introduction of AI-based supportive medical diagnostics. We will ensure that governance requirements for data sharing support the development of the, hopefully, trustworthy AI-Mind solutions.

Throughout the project lifecycle, we will provide continuous governance and assurance for data sharing relating to quality, security, trust and transparency. The requirements and current barriers for cross-border sharing of prospective data to support a future European AI supportive diagnostic decision-making tool have been addressed. The study design and administration are in line with existing European and international regulations (WP1). The goal is to create governance and assurance frameworks that will support data sharing in a trusted, safe and sustainable manner (see Deliverable 1.3). Additionally, to be able to fully achieve the expected impact of the project, potential future legal barriers for implementing the AI-tools in a clinical setting have been and will be continuously addressed.

Amongst others, legal and socio-ethical assessments have to consider issues related to liability and accountability for the tools' performance, general health law requirements, patient rights, and regulations regarding medical devices and the processing of personal data.

